## Abbreviations

Table 1: Abbreviations and Definitions

|                   |  |
|-------------------|--|
| ADR               | Adverse Drug Reaction                        |
| AE                | Adverse Event                                |
| AESI              | Adverse Event of Special Interest            |
| ATC               | Anatomical-Therapeutic-Chemical              |
| BATP              | Booster Active Trial Phase                   |
| BEAP              | Booster End of Active Phase                  |
| BFAS              | Booster Full Analysis Set                    |
| BFU               | Booster Follow-up visit                      |
| BIAS              | Booster Immunogenicity Analysis Set          |
| BMI               | Body Mass Index                              |
| BN                | Bavarian Nordic                              |
| BV                | Booster Visit                                |
| CI                | Confidence Interval                          |
| CSR               | Clinical Study Report                        |
| DL                | Detection Limit                              |
| EAP               | End of Active Phase                          |
| ECG               | Electrocardiogram                            |
| eCRF              | electronic Case Report Form                  |
| ELISA             | Enzyme-Linked Immunosorbent Assay            |
| ELISPOT           | Enzyme-Linked Immuno Spot Technique          |
| FU                | Follow-up visit                              |
| GMFI              | Geometric Mean Fold Increase                 |
| GMSFU             | Geometric Mean Spot Forming Units            |
| GMT               | Geometric Mean Titer                         |
| HCG               | Human Choriogonadotropin                     |
| HN                | Above normal range                           |
| IFN- $\gamma$     | Interferon-gamma                             |
| IgA               | Immunoglobulin A                             |
| IgG               | Immunoglobulin G                             |
| IL-4              | Interleukin 4                                |
| LN                | Below normal range                           |
| Inf.U             | Infectious Unit                              |
| Log 10 | Logarithm base 10                            |
| Max               | Maximum                                      |
| MCH               | Mean Corpuscular Hemoglobin                  |
| MCHC              | Mean Corpuscular Hemoglobin Concentration    |
| MCV               | Mean Corpuscular Volume                      |
| MedDRA            | Medical Dictionary for Regulatory Activities |
| Min               | Minimum                                      |

---

|        |  |
|--------|--|
| MVA-BN | Modified Vaccinia Ankara – Bavarian Nordic |
| n      | Number of Observations                     |
| PBMC   | Peripheral Blood Mononuclear Cells         |
| PRNT   | Plaque Reduction Neutralization Test       |
| PT     | Preferred Term                             |
| RSV    | Respiratory Syncytial Virus                |
| SAE    | Serious Adverse Event                      |
| SAP    | Statistical Analysis Plan                  |
| SAS    | Statistical Analysis System                |
| SD     | Standard Deviation                         |
| SFU    | Spot Forming Units                         |
| SMT    | Safety Monitoring Team                     |
| SOC    | System Organ Class                         |
| SOP    | Standard Operating Procedure               |
| TEAE   | Treatment-Emergent Adverse Event           |
| V      | Visit                                      |
| WBC    | White Blood Cells                          |
| WHO-DD | World Health Organization Drug Dictionary  |

---

## General Definitions

### Booster Vaccinated/Treated Subjects

A subject is considered vaccinated or treated once they have received any dose of the booster vaccination.

### Booster Study Day

For this sub-study, the day of the booster vaccination is defined as Day 0, the following as Day 1, and so on. Equally, the day before the booster vaccination in the screening period is defined as Day -1, and so on. A new study day begins always at midnight regardless of the time of the booster vaccination.

### Booster Baseline

If not otherwise specified, “booster baseline” refers to the last measurement prior to the booster vaccination, which is performed on booster visit (BV) 1 (approximately 12 months from the first vaccination in the main study). In case of missing vital event data at the first treatment visit, the booster screening vital event data may be used to impute baseline values. These data will be summarized as baseline data without specifying the visit from which the data were derived. However, in cases where no pre-treatment values exist for a baseline parameter, the subject will be considered as having no baseline, and post-baseline changes will not be able to be calculated and will be excluded from analyses.

### Main Baseline

The main study baseline (described as “main baseline” in this document) refers to the last measurement before first vaccination with trial vaccine in the main study. This is either at Visit 1 or at Screening Visit (or latest re-screening) as applicable.

### Booster Screening Phase

Time period from the booster screening visit (BV0) until the booster vaccination visit (BV1). This could include any unscheduled visits during the screening period up to the booster vaccination.

### Booster Active Trial Phase (BATP)

Time period covering from BV1 until the visit approximately 4 weeks later (Booster End of Active Phase (BEAP)); whether this occurs at the final study visit or at an early termination visit). This could include any unscheduled visits up until final visit of the booster active trial phase. This is also the vaccination period of the booster sub-study.

## **Booster Follow-Up Trial Phase**

Time period between the BEAP and the final study visit. Note that for subjects who do not return for booster sub-study follow-up visits (BFU), there may be no BFU phase data available.

### **Treatment Emergent Adverse Event (TEAE)**

A TEAE is an adverse event with an onset either on or after the day of the booster vaccination, or within the 28 days following the booster vaccination. Note that serious AEs are also considered treatment-emergent after 28 days (see below).

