### **Treatment-Emergent Adverse Events (TEAE)**

An Adverse Event (AE) with onset either on the day of a vaccination, but after the vaccination or within the 28 days following a vaccination. Note that serious AEs are also considered treatment-emergent after 28 days (see below).

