## 2.6.2 Safety Endpoints

The safety endpoints are:

- Occurrence, relationship to the trial vaccine and intensity of any serious adverse event (SAE).
- Occurrence of any Grade 3 or higher adverse events (AE) possibly, probably or definitely related to the trial vaccine within 4 weeks after the booster vaccination.
- Occurrence, intensity and duration of solicited local AEs during the 8-day period (day of vaccination and the following 7 days) after the booster vaccination.

---

- Occurrence, relationship to the trial vaccine, intensity and duration of solicited general AEs during the 8-day period (day of vaccination and the following 7 days) after the booster vaccination.
- Occurrence, relationship to the trial vaccine and intensity of unsolicited non-serious AEs within 4 weeks after the booster vaccination.

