#### **4.3.3 Assignment of AEs to Trial Phase**

Each AE will be assigned to the booster active trial phase (BATP) or booster follow-up (BFU) phase using date/time of vaccination and date/time of onset of the AE:

- All AEs starting at or after the booster vaccination but before the BEAP visit will be assigned to the booster active trial phase. For subjects who missed the BEAP visit, AEs within the booster vaccination + 28 day will also be assigned to the BATP.
- Any AEs starting after the booster vaccination but are not assigned to the BATP belong to the BFU period.

If onset time is missing and start date of AE coincides with the date of vaccination, the AE will be assigned to the BATP.

Each AE starting on or after the booster vaccination not matching the definition of a solicited AE is defined as an unsolicited AE. If a solicited AE begins outside of the 8-day period following the booster vaccination it will be considered an unsolicited AE regardless of the preferred term (PT). If start time of the AE is missing and start date coincides with date of vaccination, it will be

---

regarded as a treatment-emergent AE. If the start date is (partially) missing the AE will be regarded as a treatment-emergent AE following the worst-case principle.

Worst-case principle:

To avoid a potential misclassification of an AE to the BATP, if an imputed start date corresponds to the first of the month or to the first of the year, and matches the month and year of the booster vaccination date, then the AE will be assigned to the BATP. If the AE cannot be assigned to either phase because of a (partially) missing start date then it will be assigned to the BATP.

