## **4.5.8 Adverse Events**

A summary table will be presented as an overview of local and general solicited AEs and unsolicited AEs during the BATP. This summary table will present the number and percentage of subjects who had at least one event as well as the corresponding total number of events for:

- At least one AE documented
- Any TEAE
- Non-serious TEAEs
- SAEs
- Related TEAEs
- TEAEs Graded  $\geq 2$
- TEAEs Graded  $\geq 3$
- Related TEAEs Graded  $\geq 3$
- Related SAEs
- AEs leading to withdrawal from the trial
- Deaths

For the BATP and BFU Phase, all AEs will be listed by subject, including SOC and PT for the BFAS. Any non-serious AE with onset later than 28 days after the booster vaccination will not be included in summary tables but will be included in the listing and will be flagged accordingly as non-treatment-emergent.

---

According to the clinical trial protocol no new AEs should be reported during the BFU Phase, except SAEs, but if any are reported then they will be listed but considered non-treatment-emergent and no summary will be presented.

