### **Serious Adverse Events**

All SAEs (solicited and unsolicited) with onset from booster vaccination up to and including BEAP will be summarized by SOC and PT. Related SAEs and SAEs which occurred during the BFU Phase will be presented in a similar fashion.

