### **Pre-treatment Adverse Events**

AEs recorded after signing the informed consent form, but before administration of the booster vaccine, are considered pre-treatment AEs. These pre-treatment AEs will be presented in a subject listing.

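### The booster SAP's TEAE definition is open-ended and takes in pre-injection events; other rules contain most of the effect, but the BEAP boundary still misplaces events around day 28 and must be aligned

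*SAP*

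**What the plan says.** The SAP document contains a main-trial SAP and a booster sub-study SAP. The booster SAP sets AE timing in several places:

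- **General Definitions, TEAE:** "onset either on or after the day of the booster vaccination, or within the 28 days following the booster vaccination". The next sentence adds that serious AEs remain treatment-emergent beyond 28 days.
- **Section 2.6.2, endpoints:** "unsolicited non-serious AEs within 4 weeks after the booster vaccination". The related Grade 3 or higher endpoint is also limited to 4 weeks. The SAE endpoint has no time limit.
- **Section 4.3.3, phase assignment:** "All AEs starting at or after the booster vaccination but before the BEAP visit will be assigned to the booster active trial phase". Also: "For subjects who missed the BEAP visit, AEs within the booster vaccination + 28 day will also be assigned to the BATP". Any other post-booster event belongs to follow-up.
- **Section 4.5.8, table rule:** "Any non-serious AE with onset later than 28 days after the booster vaccination will not be included in summary tables". Such events are flagged non-treatment-emergent. New non-serious AEs reported in follow-up are likewise listed only. The overview, unsolicited TEAE and related Grade 3 or higher tables are restricted to the active phase.
- **Section 4.5.8, Serious Adverse Events:** tabulated "with onset from booster vaccination up to and including BEAP". Follow-up SAEs are to be presented similarly.
- **Section 4.5.8, Pre-treatment Adverse Events:** events after consent "but before administration of the booster vaccine, are considered pre-treatment AEs".

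The main SAP defines a TEAE as an AE "with onset either on the day of a vaccination, but after the vaccination or within the 28 days following a vaccination". Its Section 3.3.3 counts events starting at the EAP visit within the second vaccination period.

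The BEAP window is day 28 to 35 after the booster, with target week 4 (protocol Section 1.7; booster SAP Appendix 6.2).

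**The concern.** The first limb of the booster definition has no end, which makes its 28-day limb redundant. It also lacks the main SAP's condition that a booster-day event must start after the injection. Such events can arise, because the protocol has AEs recorded at BV1 before vaccination (Section 4.2.2.2). As worded, the definition contradicts both the day-28 flag and the pre-treatment rule in Section 4.5.8. The definition of a related AE is built on TEAE, so the fault carries over.

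Separately, the active phase ends at a visit whose date varies between subjects, while the two time-limited unsolicited and Grade 3 or higher endpoints are fixed at 4 weeks. If the visit date and the endpoint window disagree, the tables do not report exactly the stated endpoint. A programmer then has to decide which sentence overrides which.

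**Working it through.** There is no plan figure to reproduce. The check applies each rule to onset days counted from the injection (day 0).

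**Inputs:** 4 weeks = 28 days (Section 2.6.2); table cap at day 28 for non-serious AEs (4.5.8); active phase before BEAP (4.3.3); SAE table through BEAP (4.5.8); BEAP on day 28 to 35 (Appendix 6.2).

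**Reference window:** days 0 to 28 inclusive = 29 onset days.

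With BEAP on day *b* and onsets compared by date:

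- active phase under 4.3.3: days 0 to *b* − 1, that is *b* days;
- SAE table under 4.5.8: days 0 to *b*, that is *b* + 1 days;
- non-serious tables (4.3.3 and the day-28 cap together): days 0 to min(*b* − 1, 28).

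| BEAP | 4.3.3 active phase | SAE table | Non-serious tables |
|---|---|---|---|
| day 28 | 0–27 (28 days) | 0–28 (29) | 0–27 (28) |
| day 30 | 0–29 (30) | 0–30 (31) | 0–28 (29) |
| day 35 | 0–34 (35) | 0–35 (36) | 0–28 (29) |
| missed | 0–28 (29) | no BEAP date | 0–28 (29) |

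**Non-serious AEs.** For BEAP on days 29 to 35, or missed, the tables match the 4-week endpoint exactly. For BEAP on day 28, one onset day is lost: (29 − 28)/29 = 1/29 = 3.4%. For a BEAP held at early termination on day *b* < 28, which the active-phase definition allows, the shortfall is (29 − *b*)/29. Follow-up visits seek only new SAEs and changes to ongoing events (Appendix 6.2, footnote 2). The realistic day-28 case is therefore an event that starts on the visit date and is reported at that visit.

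**Pre-injection events.** Section 4.3.3 starts the active phase at the injection, and the unsolicited table needs both TEAE status and active-phase onset. A known pre-injection event therefore meets the literal TEAE definition but stays out of that table.

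**SAEs on the BEAP day.** Section 4.3.3 places them in follow-up and 4.5.8 in the active phase. Since 4.5.8 also presents follow-up SAEs, one event could appear in both.

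**Related Grade 3 or higher.** The day-28 cap covers only non-serious events. A serious related Grade 3 event on day 31 enters the active-phase table if BEAP is on day 35 but not if it is on day 30, although the endpoint stops at 4 weeks in both cases.

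**The case against.** The strongest reply is that the rules apply together. The sentence after the TEAE definition carries only serious AEs past 28 days, so a limit for the rest is implied. Section 4.5.8 then states it for the tables, and it agrees with the 4-week endpoint. Pre-injection events are classed as pre-treatment and listed. The longer window for SAEs is deliberate. All of this stands.

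A reader might go further and infer any of the following, which the documents do not support:

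- **Non-serious counts could run to day 34 or without end.** Ignoring the day-28 cap would give (35 − 29)/29 = 21% more onset days for a day-35 BEAP, or (32 − 29)/29 = 10% for day 32. The cap is an explicit table rule, so these are not results of the plan.
- **Subjects who miss BEAP get a shorter window.** With the cap, they have the same days 0 to 28 as subjects seen on days 29 to 35.
- **Booster and main-trial rates rest on different windows.** The main SAP has the same structure: assignment up to EAP (Section 3.3.3) and a 28-day table cap (Section 3.5.8). The difference is that the main SAP includes an event starting at EAP.

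It can also be said that Section 4.3.3 works by date and time, so a day-28 onset before the clinic visit might still count. That is possible, which is why 1 of 29 is an upper bound. The sub-study's comparisons are also descriptive (Section 4.1).

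**Conclusion.** The TEAE definition is wrong as written and should be corrected, but it does not by itself let non-serious tables run past day 28. Three boundary faults survive every other rule in the plan:

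1. A non-serious onset at or after a day-28 BEAP is left out of the tables although the endpoint includes it and a subject who missed BEAP would keep it. An early-termination BEAP shortens the window further.
2. SAEs with onset on the BEAP day have two classifications.
3. Serious related Grade 3 or higher events after day 28 are tabulated or not according to the BEAP date.

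The first is at most 1 of 29 onset days, about 3%, for a subject whose BEAP falls on day 28, and zero for BEAP on days 29 to 35. These are shares of onset days. The documents give neither AE onset rates nor the distribution of BEAP dates, so no expected event count can be stated. Severity is minor.

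**What to change.** - Replace the booster TEAE definition with the main SAP's form: onset on the booster day after the injection, or within 28 days after it. Keep SAEs treatment-emergent regardless of day, but count them from the injection rather than from BV1.
- In Section 4.3.3, assign non-serious AEs to the active-phase tables from injection to day 28 inclusive for every subject, whether or not BEAP was attended and whenever it took place.
- For SAEs, use one boundary, up to and including BEAP, in Sections 4.3.3 and 4.5.8.
- Tabulate related Grade 3 or higher AEs over the endpoint's 4-week window rather than over the active phase.

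The cost is SAP wording and one date rule. No new data are needed. A few events with onset around days 28 to 35 would change table.

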### **Serious Adverse Events**

All Serious Adverse Events (SAEs) from BV1 to the last follow-up visit are considered as treatment-emergent, regardless of the day of onset.

### **Related AE or Adverse Drug Reaction (ADR)**

Treatment-related AEs are defined as TEAEs determined by the investigator to be possibly, probably, or definitely caused by MVA-BN-RSV. TEAEs with an unknown or missing causality also constitute treatment-related AEs. In case of missing causality assessments, a TEAE will be considered as related for the summaries.

### **Nominal Titer**

The MVA-BN-RSV (Respiratory Syncytial Virus) vaccine is formulated at a nominal titer of  $5 \times 10^8$  Inf.U per dose (0.5 mL). The actual titer will be determined in stability testing.

### **Geometric Mean Titer and Geometric Mean Spot Forming Units**

The Geometric Mean Titer (GMT) and Geometric Mean Spot Forming Units (GMSFU) are calculated by taking the antilogarithm of the mean of the  $\log_{10}$  transformed titers, and Spot Forming Units, respectively.

### **Detection Limit (DL)**

The limit from where a positive signal can be measured in immunogenicity assays. Refer to Appendix 6.1 for DLs of the planned tests.

### **(Sero)Negative and (Sero)Positive Results**

For each immunogenicity assay, a negative result is defined as a titer below the DL, while a positive result is a titer equal to or above the DL.

## Response

For each immunogenicity assay, a response to the vaccine (applicable only for post baseline visits) is defined as either the appearance of a positive result for subjects with a negative result at baseline, or an increase by a factor of at least 2 compared to baseline for subjects with a positive result at baseline. Response status is applicable only for post baseline visits and is not calculated for subjects with missing baseline titer. Main study response is defined based on the main baseline. Booster sub-study response is defined based on the booster baseline. Post baseline visits include Visit (V) 1b, V2, V3, V3b, V4, end of active phase (EAP) visit, follow-up visit (FU) 1, and FU2 from the main study; BV1b, BV2, BEAP visit, BFU1, BFU2 and BFU3 from the booster sub-study.

The response rate at each post baseline visit is the percentage of subjects who have a positive response status out of the number of subjects with a non-missing response status at that visit.

## Responder

A subject is an ELISPOT responder to the vaccine in a particular test agent (F pool, G(A) pool, G(B) pool, N pool, M2 pool, RSV Virus) if the subject has a response for at least two post baseline visits (V1b, V2, V3, V3b, V4 from the main study; BV1b, BV2 from the booster sub-study) within the same test agent. The responder evaluation applies only to subjects with at least two post baseline results available.

The responder rate for each test agent F pool, G(A) pool, G(B) pool, N pool, M2 pool, RSV Virus) is the percentage of subjects who are responders to the relevant test agent out of the number of subjects with a non-missing responder status.

## Individual peak titer

The individual peak titer is the maximum of titers recorded on V1, V2, V3, V4, and EAP visit from the main study, BV2 and BEAP visit from the booster sub-study. Since V1b, V3b, and BV1b samples are only collected for the PBMC subgroup, they will be excluded from the peak titer selection.

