## 7.1 Systemic Humoral Immune Responses

Serum samples will be collected as outlined in the trials procedure schedule in [Section 1.6](#).

All samples for immunogenicity testing obtained on vaccination visits will be collected prior to vaccination.

The procedures for the immunogenicity tests performed are outlined in [Sections 7.1.1](#) and [7.1.2](#) below.

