### 7.1.2 RSV-specific PRNT

Two PRNTs will be performed to determine RSV-specific neutralizing antibody titers against RSV strain A and B, respectively. Details on the procedures can be found in SOP [REDACTED] (for strain A) "PRNT to determine RSV A Strain Specific Neutralizing Antibody Titers in Human Serum Samples" and [REDACTED] (for strain B) "PRNT to determine RSV B Strain Specific Neutralizing Antibody Titers in Human Serum Samples".

The individual peak titer is calculated as the maximum of all post baseline titer measurements for that individual. The individual peak titer is only missing if all post baseline titers are missing, otherwise the maximum of the available post baseline titers is used.

The GMT is calculated per visit as well as based on individual peak titers by taking the antilogarithm of the mean of the  $\log_{10}$  titer transformations. The GMFI is calculated analogously per post-baseline visit as the geometric mean of the individual fold increases, i.e. the subjects' post-baseline titers at Visit X, divided by their corresponding baseline titer.

The RSV-specific antibody response rate (applicable only to post-baseline visits) is calculated per visit as well as based on individual peak titers and is defined as the percentage of subjects with antibody response based on the total number of subjects with test results available. The response status is assessed with regard to the corresponding baseline (Visit 1) test result.

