### **Active Trial Phase**

The active trial phase is defined as the trial phase starting with and including Visit 1 and ending with and including EAP (End of active trial phase) (V3 + 28-35 days).

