**Individual peak titer**

The individual peak titer is the maximum of titers recorded on V1b, V2, V3, V3b, V4, EAP Visit.

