**Table 2 Treatment Groups in the Main Study**

| Group        | N          | Age [years] | Volume per dose [mL] | 1 st vaccination
Day 0
[Inf.U] | 2 nd vaccination
Day 28
[Inf.U] | Route |
|--------------|------------|-------------|----------------------|---|--|-------|
| 1     | 78         | $\geq 55$   | 0.5                  | $1 \times 10^8$                                 | Placebo  | IM    |
| 2     | 89         | $\geq 55$   | 0.5                  | $1 \times 10^8$                                 | $1 \times 10^8$                                  | IM    |
| 3     | 80         | $\geq 55$   | 0.5                  | $5 \times 10^8$                                 | Placebo  | IM    |
| 4     | 90         | $\geq 55$   | 0.5                  | $5 \times 10^8$                                 | $5 \times 10^8$                                  | IM    |
| 5     | 83         | $\geq 55$   | 0.5                  | Placebo   | Placebo  | IM    |
| Total | 420 |             |                      |   |  |       |

Approximately one year after their first vaccination in the main study, 86 subjects in two selected treatment groups of the main study (Group 1 and Group 3) are planned to be recruited to participate in the booster sub-study. They will receive a single booster vaccination using the same MVA-BN-RSV dose they received during the main study. Subjects will be followed up for 12 months after their booster vaccination. Out of these 86 subjects, approximately 26 will be recruited from the PBMC subgroup (approximately 13 subjects for each of the two selected dose

---

groups). The selection of the treatment groups to be included in the booster sub-study is based on the results of the main study.

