#### **4.6 Alterations in SAP from the Clinical Trial Protocol**

RSV-specific memory B cells analyses are not covered in this SAP, but will be addressed in detail in an SAP amendment after further assay development.

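### The booster SAP's main-study peak titer wrongly includes the pre-vaccination V1 sample; separately, the peak and ELISPOT responder windows differ between phases and need a footnote if shown together

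*SAP*

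**What the plan says.** - **Booster SAP, General Definitions, Individual peak titer:** "The individual peak titer is the maximum of titers recorded on V1, V2, V3, V4, and EAP visit from the main study". The sentence then names BV2 and BEAP for the sub-study. The next sentence drops V1b, V3b and BV1b because only the PBMC subgroup has them.
- **Protocol 7.1:** "All samples for immunogenicity testing obtained on vaccination visits will be collected prior to vaccination". V1 is a vaccination visit, and the booster SAP names it as the main baseline.
- **Protocol 7.1.1, 7.1.2 and 7.2:** the peak is taken over post-baseline titers. Section 7.1.2 adds: "The individual peak titer is only missing if all post baseline titers are missing".
- **Main-study SAP, General Definitions:** "The individual peak titer is the maximum of titers recorded on V1b, V2, V3, V3b, V4, EAP Visit".
- **Booster SAP, Response:** "Post baseline visits include Visit (V) 1b, V2, V3, V3b, V4, end of active phase (EAP) visit", followed by later visits. V1 is not listed.
- **Booster SAP 4.6** has one entry: "RSV-specific memory B cells analyses are not covered in this SAP".
- **Booster SAP, Responder:** two or more responses are needed, from V1b, V2, V3, V3b and V4 in the main study, or from BV1b and BV2 in the sub-study. Main-study SAP 3.4.3 has no ELISPOT sample at V3.
- **Booster SAP 2.1:** "86 subjects in two selected treatment groups of the main study (Group 1 and Group 3) are planned to be recruited". In both groups the second main-study injection was placebo.
- **Booster SAP 4.5.7** puts main-study and booster sampling points into one PRNT strain A summary so that the phases can be compared, and handles the other assays in a similar way. Section 2.6.1 lists peak-based GMT and response rate for every antibody assay. Section 6.3 marks the IFN-γ responder tables as topline.

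**The concern.** A peak that a pre-vaccination sample can set is not purely a measure of response. The booster SAP's Introduction says the plan will be followed in full, so V1 would be programmed as written. It can only raise the main-study peak, and the booster peak gets no matching addition.

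The second issue concerns reading the results. A maximum over more visits tends to be larger, and two responses out of four chances are easier to reach than two out of two. If main-study and booster peaks or responder rates stood next to each other, boosting could look weaker than it is, and the sub-study's aim is to show that responses can be boosted. All these quantities are descriptive and no test uses them, so what is at stake is a misleading display rather than a wrong inference.

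**Working it through.** **1. The plan's own figure.** Booster SAP 4.1 gives a paired comparison with n = 40, limit 0.08 log10, SD of differences 0.168 and one-sided 0.025. Noncentrality is 0.08 × √40 / 0.168 = 3.01. Power is 85.4% by normal approximation and 83.6% by noncentral t, in agreement with the stated >80%. Only the SD is used below: the per-visit within-subject SD is 0.168/√2 = 0.119 log10. Kinetics, error correlation and ELISPOT response probabilities are assumptions.

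**2. The definitions compared.**

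| Source | Visits in the peak | Own baseline included? |
|---|---|---|
| Protocol 7.1.1–7.2 | all post-baseline | no |
| Main-study SAP | V1b, V2, V3, V3b, V4, EAP | no |
| Booster SAP, main-study half | V1, V2, V3, V4, EAP | yes |
| Booster SAP, booster half | BV2, BEAP | no |

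V1 cannot stand for V1b, because the next sentence excludes V1b.

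**3. Size of the V1 effect.** The expected maximum of 2, 4 and 5 standard normals is 0.564, 1.029 and 1.163 SD. With flat titers and independent errors, V1 adds (1.163 − 1.029) × 0.119 = 0.016 log10, a ratio of 1.04, and sets the peak in 20% of subjects. With a 1.5- to 2-fold rise it sets the peak in 0.1–4% and adds 0.000–0.002 (table below). The peak response rate is unchanged: V1 divided by itself is 1, below the 2-fold threshold, and a negative V1 cannot count as a new positive.

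**4. Size of the window effect on the peak.** The active phase is defined as "ending with and including EAP (End of active trial phase) (V3 + 28-35 days". In Groups 1 and 3, days since the only active main-study dose are therefore:
- V4: 28+12 to 35+16 = 40–51
- EAP: 28+28 to 35+35 = 56–70
- BEAP, after the booster: 28–35

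For flat titers and independent errors, four visits against two gives (1.029 − 0.564) × 0.119 = 0.055 log10, a ratio of 1.14. Simulation used 1,000,000 draws per scenario, normal errors, and equal true responses in the two phases (BV2 and BEAP take the V2 and V3 means). Each cell shows error correlation 0 / 0.5.

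| Log10 rise at V2, V3, V4, EAP | V1 part | Window part | Main/booster peak GMT ratio from window |
|---|---|---|---|
| flat: 0, 0, 0, 0 | 0.0159 / 0.0113 | 0.0551 / 0.0390 | 1.14 / 1.09 |
| 1.5-fold, no waning: .176 throughout | 0.0010 / 0.0001 | 0.0554 / 0.0392 | 1.14 / 1.09 |
| 1.5-fold, mild: .176, .176, .141, .123 | 0.0014 / 0.0003 | 0.0363 / 0.0213 | 1.09 / 1.05 |
| 1.5-fold, strong: .176, .150, .088, .062 | 0.0023 / 0.0006 | 0.0223 / 0.0098 | 1.05 / 1.02 |
| 2-fold, strong: .301, .256, .150, .105 | 0.0003 / 0.0000 | 0.0101 / 0.0026 | 1.02 / 1.01 |

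A within-subject SD of 0.06 or 0.168 would move the flat, independent-error ratio from 1.14 to 1.07 or 1.20. Peak response rates (main vs booster, 1.5-fold rise) run from 49% vs 35% (no waning, independent errors) to 22% vs 21% (strong waning, correlation 0.5). Comparing max(V2, V3) with max(BV2, BEAP) gives a difference of 0.000 in every scenario.

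**5. Size of the window effect on the ELISPOT responder.** At a per-visit response probability of 0.6 with independent visits:
- Main study, two of four: 1 − 0.4⁴ − 4 × 0.6 × 0.4³ = 82%
- Booster, two of two: 0.6² = 36%

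With latent correlation 0.5 and decline to 0.5 and 0.4 at V3b and V4, the rates are 64% vs 44%. With correlation 0.8 and decline to 0.3 and 0.2, they are 53% vs 50%. At about 13 subjects per group, 6/13 has an exact 95% interval of 19–75%.

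**The case against.** The strongest reply on V1 is that it changes almost nothing. A reader might infer that a peak-based fold increase could never fall below 1. But the plan has no such quantity: fold increase is defined visit by visit, and only GMT and response rate use the peak. A subject with a V1 titer and nothing later would gain a peak that the protocol calls missing. Booster entry, however, requires completion of all main-study vaccinations and serum is mandatory at V3, so this should hardly occur. The conflict with the post-baseline visit list is also weak, since that list belongs to the definition of response. All of this stands. It limits the consequence but does not remove the contradiction with the protocol. The October 2017 SAP addendum is not among the documents and might have changed the main-study SAP's peak, but it would not reconcile the booster SAP with protocol Edition 4.0, on which that SAP says it is based.

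On the windows, the reply is that they are not a mistake. Each peak ends at its own end-of-active-phase visit, protocol 7.3 sets the two-visit responder rule, and the booster schedule has only two PBMC draws after vaccination and before BEAP. That stands. So does the point about layout. The protocol synopsis asks for peaks separately by phase, no table title names peak titer, the responder paragraph in 4.5.7 promises only a presentation by group, and the table shells are in a separate document. A reader might take side-by-side peak or responder columns as settled; the text makes them likely but does not state them.

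**Conclusion.** The V1 entry is wrong as written: it contradicts the protocol and the main-study SAP, does not match the booster half of its own sentence, and is undeclared. It is probably an editing slip. Confidence is high and the effect is minor, about 0.016 log10 in main-study peak GMT with flat titers and 0.000–0.002 with a 1.5- to 2-fold rise.

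The unequal windows are a caution about comparability, not an error. Confidence is moderate, because the display is inferred. With equal true responses they can make the booster value look lower, by a negligible to moderate amount: peak GMT ratio 1.01–1.14 at the assumed SD of 0.119, and responder rates from 53% vs 50% to 82% vs 36%. A reader might infer that the booster would always look clearly weaker. The strong-waning scenarios do not support that, and the smaller responder gaps are well within noise at about 13 per group.

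Per-visit GMTs, fold increases and response rates are unaffected. So are the paired main-versus-booster ratios, which already use comparable times after vaccination, and the Group 3/Group 1 comparisons, where both groups share the same windows.

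**What to change.** Delete V1 from the booster SAP's definition, so that the main-study peak is the maximum of V2, V3, V4 and EAP. This costs one edit and one line of derivation code.

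If main-study and booster peak or responder values appear together, add a footnote giving the windows: four against two post-vaccination visits for the peak, and two of four against two of two sampled visits for the responder. Alternatively, add supplementary matched values: max(V2, V3) against max(BV2, BEAP), and responder status on V1b and V2 against BV1b and BV2. The scheduled day ranges already agree (7–9, 12–16 and 28–35). Keep the protocol definitions as the main ones. No new data are needed; the price of the matched option is a second, labelled main-study value that departs from the protocol's definition.
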